2.2 Objectives

The primary objectives are to determine the feasibility, design, and implementation plan for a subsequent randomised controlled trial to evaluate the effectiveness of the PET for increasing uptake of COVID-19 and Flu vaccination.

The secondary objectives are to determine (i) an estimate of COVID-19 and Flu vaccination uptake, its variation by population group, and other parameters to design a subsequent randomised controlled trial; (ii) the feasibility and practicality of implementing the PET; and (iii) the appropriate level of support needed for health care providers at site-level to ensure successful implementation of the PET and to identify supporting activities needed to implement interventions for COVID-19 and Flu vaccinations.

3 Study Methods

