3.4 Framework

- Primary analysis on uptake will report 95% CI, with no p-values to test superiority because this is a feasibility study that is not powered on superiority.
- Secondary analysis on other outcomes will use descriptive analysis.

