4.1 Confidence intervals and P values

For the primary outcomes two-sided 95% confidence intervals will be used for uptake in each arm, and for the comparison between arms. For secondary outcomes confidence intervals (CIs) will be presented with no adjustment for multiplicity. For all other outcome point estimates, 95%CIs will be reported and no a priori statistical significance or decisions based on cut points for p-values will be used.

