6.3 Analysis methods

6.3.1 Primary analysis

For the primary analysis, uptake of COVID-19 and Flu vaccination will be presented in each arm on an intention to treat basis. The Flu vaccination trial will have both sms and letter group combine as one trial.

We will assess the individual-level-randomised component. This analysis will include all patients who are eligible for the intervention, and who were randomised to receive one of two workflows on an individual basis (standard of care or the PET). All patients from first group of GPs (n=3) in both study periods, and only patients from second group (n=3) who are eligible in the second period (i.e., any eligible patient from first period in the second group of GPs who was vaccinated in the first period would not be part of the analysis sample) will be included. Uptake (from time of randomisation) will be estimated overall. Uptake 95% CIs will be obtained

based on binomial assumption, as well as from a mixed-effects model that allows for hierarchical (random effects) variation by GP. Logistic regression with adjustment described below will be used to estimate the marginal odds ratio of the PET compared with standard of care, and a profile-likelihood ratio confidence interval for the odds ratio will be reported.

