6.3.2 Adjustments

Adjusted estimates will use:

- GP (categorical)
- Age (continuous)
- Sex (male/female)

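### SAP 6.3.1 calls the primary between-arm estimate a marginal odds ratio, but the adjusted logistic model it specifies gives a conditional one

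*SAP*

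**What the plan says.** For the primary outcome, SAP section 4.1 says that "two-sided 95% confidence intervals will be used for uptake in each arm, and for the comparison between arms". Section 6.3.1 defines that comparison: "Logistic regression with adjustment described below will be used to estimate the marginal odds ratio of the PET compared with standard of care", and adds that "a profile-likelihood ratio confidence interval for the odds ratio will be reported". The adjustment is listed in section 6.3.2: GP as a categorical term, age as a continuous term, and sex.

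The mixed-effects model with GP random effects in section 6.3.1 is given for the uptake confidence intervals, not for the odds ratio. Section 6.3.5 adds exploratory adjustment for ethnicity and deprivation. The SAP nowhere mentions standardisation, weighting, marginal effects, or a delta-method or bootstrap interval. Section 3.4 says the primary analysis carries "no p-values to test superiority because this is a feasibility study that is not powered on superiority".

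**The concern.** The stated target and the stated method do not match. A logistic model with GP, age and sex as covariates returns an odds ratio for PET versus standard of care among patients with the same GP, age and sex. A marginal odds ratio compares average uptake in the randomised population if all had PET with average uptake if none had. These are different numbers unless the effect is null or the covariates are unrelated to uptake. If the plan is followed as written, a conditional estimate and its interval are reported under a marginal label.

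This is the only between-arm effect measure specified for the primary outcome, and section 2.2 lists among the study's aims the "other parameters to design a subsequent randomised controlled trial". A reader told that the odds ratio is marginal may fairly apply it to crude control uptake when planning the next trial, and would then expect too large a difference in uptake.

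**Working it through.** **No figure to reproduce.** The SAP gives no uptake, effect size, number of patients or covariate strength; section 3.3 leaves sample size to the protocol. All numerical inputs below are assumptions.

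**Step 1: what the model estimates.** The specified model is

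logit P(vaccinated) = a + b·arm + GP + age + sex.

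The reported odds ratio is exp(b), with GP, age and sex held fixed. The marginal odds ratio is [p1/(1−p1)] / [p0/(1−p0)], where p1 and p0 are the model probabilities averaged over the covariates with arm set to 1 and to 0. A profile-likelihood interval from the fit is an interval for b. It does not carry over to a function of averaged predictions without further work.

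**Step 2: size of the gap.** Replace GP + age + sex by a normal score with standard deviation SD on the logit scale. Solve a so that p0 equals the chosen control uptake, average expit(a + b + SD·z) over z to get p1 (Gauss-Hermite integration, 80 nodes), and form the marginal odds ratio. Ranges are over control uptake of 10, 20, 30 and 40%; a dash marks a cell not tabulated here.

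| Conditional OR | SD 0.25 | SD 0.5 | SD 0.75 | SD 1.0 |
|---|---|---|---|---|
| 1.0 | 1.000 | 1.000 | 1.000 | 1.000 |
| 1.2 | – | 1.188–1.195 | – | 1.163–1.179 |
| 1.5 | 1.491–1.496 | 1.467–1.484 | 1.434–1.464 | 1.399–1.439 |
| 2.0 | – | 1.925–1.960 | – | 1.775–1.855 |

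Over conditional odds ratios of 1.2 to 2.0, the marginal log odds ratio is smaller by 0.6–1.5% at SD 0.25, 2.5–5.5% at SD 0.5 and 9.6–17.3% at SD 1.0.

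**Step 3: against sampling error.** Take 30% control uptake, conditional odds ratio 1.5 and an illustrative 500 patients per arm, with the standard error of b from the expected information for (intercept, arm, z). The gap in log odds ratio is 0.04, 0.15 and 0.45 standard errors at SD 0.25, 0.5 and 1.0. It scales with the square root of the sample size: at 2,000 per arm, √(2,000/500) = 2, so it doubles to about 0.08, 0.30 and 0.90.

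**Step 4: the same fit read both ways.**
- In 1,000 simulated trials (1,000 patients, six GPs, about 30% control uptake, conditional odds ratio 1.5, covariate SD 0.49), fitting arm, GP, age and sex gave a mean arm coefficient of 0.414. The mean standardised log odds ratio from the same fits was 0.390, the median ratio was 0.945, and the standardised odds ratio was closer to 1 in all 1,000.
- In one large simulated data set (200,000 patients, conditional odds ratio 2.0, SD about 0.79, uptake about 30% versus 44%), the coefficient gave 1.99, the standardised odds ratio 1.84 and the crude odds ratio 1.83. The coefficient recovers the conditional value; the standardised and crude values sit together at the marginal one.

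**Step 5: consequence for planning.** Take control uptake 30% and conditional odds ratio 1.5. Pairing the two gives odds of (0.30/0.70) × 1.5 = 0.643, so uptake of 0.643/1.643 = 39.1% on PET. The uptake actually implied is 39.0% at SD 0.25, 38.6% at SD 0.5 and 37.6% at SD 1.0. The squared difference, which drives the sample size of an unadjusted comparison, would be overstated by about 12% at SD 0.5, from (9.13/8.64)² = 1.12, and by about 46% at SD 1.0, from (9.13/7.57)² = 1.46.

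**The case against.** The best defence is that this is loose wording, not a faulty analysis. Section 6.3.2 calls the results adjusted estimates, and the sentence before the quoted one concerns a model with GP random effects, so the authors may have written 'marginal' only to contrast with GP-specific effects. That may explain the word, but it does not make it correct: GP is itself a covariate in this model, so the odds ratio is conditional on GP as well as on age and sex.

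A second reading is that logistic regression is merely the tool and standardisation is left unsaid, so that the text is incomplete rather than contradictory. This is possible, but it sits badly with the profile-likelihood interval, which is the natural interval for a coefficient and the only one specified.

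The points on weight stand. Uptake in each arm will be reported with confidence intervals, so the planners of the next trial can take the marginal contrast from it directly, and no passage says that the adjusted odds ratio will be paired with crude uptake. At SD 0.25–0.5 that pairing would be wrong by at most 0.5 percentage points in the example above. Nothing in the SAP shows that GP, age and sex are prognostic enough to reach SD 1.0.

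**Conclusion.** The concern holds and is minor. The target named for the primary between-arm comparison is not the quantity that the specified model and interval deliver. The estimate is sound as a conditional odds ratio. Under the assumed inputs, the mislabelling hides a difference of about 1–6% on the log odds ratio scale for weak to moderate covariates (SD 0.25–0.5), and about 10–17% for strongly prognostic ones (SD 1.0). The gap is zero if PET has no effect. Since section 3.4 excludes superiority p-values and no decision rule in the SAP uses this odds ratio, the consequence is confined to how the estimate is read and reused. The mismatch itself does not depend on the assumed inputs; only its size does.

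**What to change.** Choose one of the following in SAP section 6.3.1:

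- **(a) Relabel.** Replace 'marginal' with 'conditional (GP-, age- and sex-adjusted)' and keep the profile-likelihood interval. This changes wording only; model and results stay the same.
- **(b) Keep the marginal target.** Average the fitted model's predictions over the randomised sample under each arm, form the odds ratio from the two averages, and give a delta-method or bootstrap 95% interval. Report the arm coefficient with its profile-likelihood interval alongside, as the conditional odds ratio. This takes a few extra lines of R or Stata on the same fit, and the odds ratio will usually be slightly closer to 1.

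In either case, add a sentence saying that the conditional odds ratio should not be combined with crude control uptake when planning the next trial. Neither option needs new data.

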6.3.2 Adjustments

Adjusted estimates will use:

- GP (categorical)
- Age (continuous)
- Sex (male/female)

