3.1 Trial design

The PET was designed in qualitative work packages that preceded the feasibility trial. Eligible patients from six general practitioner (GP) practices from Tower Hamlets and Newham were individually randomised 1:1 to the intervention (PET) or control (routine care) during the study. The Appt-Health workflow tool was used, but patients in the control group did not receive additional (individual level) interventions outside routine; however some “cluster-level” interventions were used including posters in surgeries. Letters were used to invite patients with no device to receive SMS invitation for flu vaccination.

To enable a comparison of the intervention to a control group at a practice level, we randomised GPs after they were recruited to the study. n=6 practices were randomised 1:1 to two groups of size n=3 vs. n=3. During a first study period, the first group of n=3 GPs received training, activation of the software, and patients were randomised. This happened for the second group of GPs in a subsequent study period.

A cluster-level analysis will use data from the first period in all n=6 GPs. The individual-randomisation comparison will use data from all GPs, with the second group contributing data from the second period only.

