6.1 Outcome definitions

6.1.1 Primary outcome

The primary outcome is vaccination uptake in patients individually randomised. This will be measured as the number (percent) of relevant SNOMED codes in eligible patients. Uptake will be measured from the time that the eligible group in each practice is identified (and randomised) until 6 months follow-up (>180 days since randomisation).

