6.1.2 Secondary outcomes

1. Vaccination uptake in patients after 3- and 9-months follow-up (>90 and >270 days). This will be measured as the number (percent) of relevant SNOMED codes in eligible patients identified during the period.
2. Mean vaccination rate after 3-, 6- and 9-months follow-up. This will be measured as the number of patients vaccinated divided by the follow-up time. Time is defined as time from randomisation until the earliest of vaccination, leaving the GP, withdrawal the consent of use of data, or death.
3. Acceptability of the intervention
 - a. To patients: Proportion of patients randomised to the intervention who engage with the PET and / or linked patient resources, as determined by user statistics logged on the software for
 - i. The SMS messaging tool (number of SMS sent)
 - ii. Number (percent) of patients who view the linked patient awareness resources
 - iii. Usage of the patient work list tool
 - b. To staff: Number and proportion of eligible patients randomised to the intervention processed using the patient work list tool
4. Feasibility of the intervention and randomisation
 - a. Number and proportion of eligible patients randomised
 - b. Clinical capacity: number of slots available for vaccination bookings for each GP surgery and each day, by appointment time
5. Feasibility of the study design for a subsequent trial

- a. Number and proportion of patients with all inclusion / exclusion data available on the electronic health records
- b. Number and proportion of patients eligible for the intervention
- c. Number and proportion of patients randomised who are sent material from the intervention (letter / sms)
- d. Number and proportion of patients eligible by vaccination status (none, first, second, with booster or without booster)
- e. Number and proportion of patients who opt out for their data to be used or withdraw from the study
- f. Number and proportion of patients who consent for further questionnaires
- g. Number and proportion of patients who are booked for a vaccination appointment
- h. Number and proportion of patients who are categorised a “failed encounter” (not booked, no more action taken)

This list only includes quantitative endpoints in the protocol. There will be additional qualitative analysis of other points in the protocol.

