6.3.5 Exploratory analysis

We will explore vaccination uptake in patients after 9-months follow-up. We will explore the cluster-randomised component of this study. The population of analysis is those identified as eligible in both groups in the first study period, from the same calendar time. Analysis of uptake will take clustering in the design into account by using generalised linear models with (normal) random intercepts, and the model will also be used to obtain an estimate of the intra-class correlation coefficient. There are several methods to analyse cluster randomised trial data and we will also explore different models and assumptions in order to propose methods for the larger trial.

We will also explore whether a per-protocol analysis would be possible, by determining feasibility to define compliance / contamination from individual randomised allocation using process data. We will explore an analysis that makes use of the comparison between period 1 and period 2 in the n=3 GPs who are activated in the second period. This analysis may be

confounded by temporal effects so is treated as an exploratory analysis.

We will also adjust estimates using additional variables ethnicity and deprivation as an exploratory analysis.

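### Earlier COVID-19 dose history is to be tabulated but is not adjusted for; adding it could modestly tighten the marginal odds ratio, provided the interval method changes too

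*SAP*

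**What the plan says.** SAP section 6.3.2 ("Adjusted estimates will use") lists three terms: practice as a category, age as a continuous variable, and sex. Section 6.3.1 applies them to the primary comparison: "Logistic regression with adjustment described below will be used to estimate the marginal odds ratio of the PET compared with standard of care". It adds that "a profile-likelihood ratio confidence interval for the odds ratio will be reported". Section 6.3.5 widens the set once: "We will also adjust estimates using additional variables ethnicity and deprivation as an exploratory analysis".

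The outcome is binary: "The primary outcome is vaccination uptake in patients individually randomised". In section 6.1.2, item 5d, under feasibility of a later trial's design, the plan will report "Number and proportion of patients eligible by vaccination status (none, first, second, with booster or without booster". That variable is absent from the baseline characteristics (5.5), both adjustment sets, the subgroups (6.3.4) and the dummy baseline table (Appendix).

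**The concern.** The outcome is whether a patient is vaccinated, and earlier vaccination is the nearest baseline counterpart of that outcome. Section 5.2 restricts entry to patients not yet vaccinated in the current season. What varies between them is therefore earlier dose history, which is fixed before allocation and can safely be used as a covariate.

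Section 3.2 allocates patients by simple randomisation within practice, so dose history is balanced only on average. Any chance difference between arms adds to the sampling variation of the effect estimate unless the model accounts for it. Sections 3.4 and 4.1 make intervals, not tests, the product of the primary analysis. At stake is the width of the interval for the COVID-19 comparison. A further gain is that the fitted model would show how far dose history explains uptake, which serves the secondary objective of collecting design parameters for the larger trial (2.2).

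**Working it through.** **No figure to reproduce.** The SAP states no sample size (3.3 refers to the protocol), no expected uptake, and no relation between dose history and uptake. Every input below is an assumption, shown as a range.

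**Step 1: prior status alone.** Take a two-level status with half of patients previously vaccinated, uptake p0 without and p1 with earlier vaccination, and mean p̄. Near the null, the variance of the marginal log odds ratio is multiplied by

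r = [½p0(1−p0) + ½p1(1−p1)] / [p̄(1−p̄)].

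The standard error (SE) of the marginal log odds ratio scales by √r; the SE of the conditional logistic coefficient scales by 1/√r. For 10% v 30%: p̄ = 0.20 and r = (0.5×0.09 + 0.5×0.21)/0.16 = 0.15/0.16 = 0.937, so √r = 0.968 and 1/√r = 1.033.

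| Uptake p0 v p1 | r | Marginal SE | Conditional SE |
|---|---|---|---|
| 10% v 15% | 0.994 | ×0.997 | ×1.003 |
| 10% v 30% | 0.937 | ×0.968 | ×1.033 |
| 5% v 35% | 0.859 | ×0.927 | ×1.079 |
| 10% v 50% | 0.810 | ×0.900 | ×1.111 |

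**Step 2: on top of practice, age and sex.** Step 1 ignores what the planned terms already explain, so the increment was simulated. Assumptions: 2,000 patients, six practices, 1:1 allocation, 1,500 runs per setting, prior status held by about half and correlated with age, overall uptake 18% to 30%, true conditional odds ratio for the PET 1.00 or 1.49. The marginal odds ratio came from averaging predictions under each arm. The ratio is the empirical SD of the marginal log odds ratio with prior status in the model, divided by that without.

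| Prior-status odds ratio | PET odds ratio 1.00 | PET odds ratio 1.49 | Fall in SE |
|---|---|---|---|
| 1.6 | 0.996 | 0.998 | 0.2-0.4% |
| 2.7 | 0.984 | 0.986 | 1.4-1.6% |
| 7.4 | 0.1014/0.1083 = 0.936 | 0.0938/0.1013 = 0.925 | about 6-8% |
| 20 | 0.870 | 0.849 | about 13-15% |

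**Step 3: the same models with the interval as planned.** A profile-likelihood interval from a logistic model is an interval for the treatment coefficient, which is conditional on the covariates. At a prior-status odds ratio of 7.4 and a PET odds ratio of 1.49, adding prior status raises the mean SE of that coefficient from 0.1068 to 0.1149 (0.1149/0.1068 = 1.076, so 7.6% wider on the log-odds scale). The coefficient moves from 0.347 to 0.401, and the share of runs with |z| > 1.96 rises from 0.897 to 0.936. Information is gained, but the interval as specified in 6.3.1 would not show it as a shorter width.

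**The case against.** The strongest reply is that three pre-specified covariates are a defensible choice, nothing in 6.3.2 is wrong, and this is a feasibility study with no superiority test. That stands as far as it goes. Randomisation keeps the estimate free of bias, a valid 95% interval already allows for chance imbalance, and the uptake intervals by arm are outside the adjusted model. It limits the importance of the point but does not remove it, because the interval is itself the primary output.

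Four further objections stand and set the limits of the point.

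- **Narrowing is not automatic.** A reader might infer that adding the term to 6.3.2 is enough. Step 3 shows the opposite under the profile-likelihood interval of 6.3.1.
- **Size.** A reader might take the variance explained by dose history alone as the gain. For example, shares of 30/20/50% with uptake 5/10/40% give a mean of 0.235 and a between-group variance of 0.0275. Then 0.0275/0.1798 = 15.3%, or 1/(1−0.153) = 1.18, as if 18% more patients had been recruited. That uses a steep assumed gradient and ignores overlap with practice, age and sex. Even so, it is only about 8% in width (√0.847 = 0.920). The SAP supplies nothing to support such a headline.
- **Scope.** The categories in 5d read as COVID-19 doses. No earlier flu vaccination variable appears anywhere in the SAP.
- **Availability.** Item 5d is a count. Tabulating patients by status needs each patient's status, so patient-level data is a strong inference, but the SAP does not say that it is linked to the randomised records or dated to the eligible list.

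**Conclusion.** This is a cheap improvement, mainly to the COVID-19 comparison; it does not correct an error. Dose history is planned to be tabulated, precedes allocation, plausibly predicts the outcome, and is in neither adjustment set. The expected fall in the SE of the marginal log odds ratio runs from under 1% to about 15%, depending on how strongly earlier doses predict uptake, and is about 6-8% at a prior-status odds ratio near 7. These figures rest on the simulated settings, not on trial data. The simulated marginal estimate lost no precision in any setting.

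A reader might infer that the planned odds ratio is biased, or that the gain is large, assured or equal in both vaccine comparisons. The SAP supports none of these.

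**What to change.** - **6.3.2:** for COVID-19, add dose history as it stood at the eligible-list date, keeping practice, age and sex. First confirm that it links to the randomised records. The date matters because the final database also holds doses given during follow-up, which are the outcome.
- **Flu:** add prior flu vaccination only if that field is in the extract; otherwise leave the Flu model as it is.
- **6.3.1:** state that the marginal odds ratio is obtained by averaging model predictions with every patient set to each arm in turn. Replace the profile-likelihood interval with a delta-method or bootstrap interval.
- **5.5 and the dummy table:** show dose history by arm.

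The cost is SAP wording, two or three extra model terms, a linkage check and a slightly more complex interval calculation. The change should be fixed before uptake by arm is examined.
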